8.3.3.1 SEVERITY OF EVENT

For adverse events (AEs), guidelines will be used to describe severity.

- **Mild** – Events require minimal or no treatment and do not interfere with the participant’s daily activities.
- **Moderate** – Events result in a low level of inconvenience or concern with the therapeutic measures. Moderate events may cause some interference with functioning.
- **Severe** – Events interrupt a participant’s usual daily activity and may require systemic drug therapy or other treatment.
-

8.3.3.2 RELATIONSHIP TO STUDY INTERVENTION

All adverse events (AEs) will be assessed for relationship to study intervention as the following:

Related – The AE is known to occur with voxelotor, such as diarrhea, nausea, abdominal pain, and there is a reasonable possibility that voxelotor caused the AE, or there is a temporal relationship between voxelotor and the event.

Not Related – There is not a reasonable possibility that voxelotor caused the event, there is no temporal relationship between voxelotor and event onset, or an alternate etiology has been established.

OR

Definitely Related – There is clear evidence to suggest a causal relationship, and other possible contributing factors can be ruled out. The clinical event, including an abnormal laboratory test result, occurs in a plausible time relationship to taking voxelotor and cannot be explained by concurrent disease or other drugs or chemicals. The response to withdrawal of the study intervention (dechallenge) should be clinically plausible. The event must be pharmacologically or phenomenologically definitive, with use of a satisfactory rechallenge procedure if necessary.

Probably Related – There is evidence to suggest a causal relationship, and the influence of other factors is unlikely. The clinical event, including an abnormal laboratory test result, occurs within a reasonable time after taking voxelotor, is unlikely to be attributed to concurrent disease or other drugs or chemicals, and follows a clinically reasonable response on withdrawal (dechallenge). Rechallenge information is not required to fulfill this definition.

Potentially Related – There is some evidence to suggest a causal relationship (e.g., the event occurred within a reasonable time after taking voxelotor). However, other factors may have contributed to the event (e.g., the participant’s clinical condition, other concomitant events). Although an AE may rate only as “possibly related” soon after discovery, it can be flagged as requiring more information and later be upgraded to “probably related” or “definitely related”, as appropriate.

Unlikely to be related – A clinical event, including an abnormal laboratory test result, whose temporal relationship to voxelotor makes a causal relationship improbable (e.g., the event did not occur within a reasonable time after taking voxelotor) and in which other drugs or chemicals or underlying disease provides plausible explanations (e.g., the participant’s clinical condition, other concomitant treatments).

Not Related – The AE is completely independent of voxelotor, and/or evidence exists that the event is definitely related to another etiology. There must be an alternative, definitive etiology documented by the clinician.

8.3.3.3 EXPECTEDNESS

The PI will be responsible for determining whether an adverse event (AE) is expected or unexpected. An AE will be considered unexpected if the nature, severity, or frequency of the event is not consistent with the risk information previously described for voxelotor in Section 2.3.1.

Expected AEs include: headache, diarrhea, abdominal pain, nausea, fatigue, rash, pyrexia

8.3.4 TIME PERIOD AND FREQUENCY FOR EVENT ASSESSMENT AND FOLLOW-UP

Example text provided as a guide, customize as needed:

The occurrence of an adverse event (AE) or serious adverse event (SAE) may come to the attention of study personnel during study visits and interviews of a study participant presenting for medical care, or upon review by the study PI.

All AEs including local and systemic reactions not meeting the criteria for SAEs will be captured on the appropriate study database form. Information to be collected includes event description, time of onset, clinician’s assessment of severity, relationship to study product (assessed only by those with the training and authority to make a diagnosis), and time of resolution/stabilization of the event. All AEs occurring while on study must be documented appropriately regardless of relationship. All AEs will be followed to adequate resolution.

Any medical condition that is present at the time that the participant is screened will be considered as baseline and not reported as an AE. However, if the study participant’s condition deteriorates at any time during the study, it will be recorded as an AE.

Changes in the severity of an AE will be documented to allow an assessment of the duration of the event at each level of severity to be performed. AEs characterized as intermittent require documentation of onset and duration of each episode.

The study coordinator will record all reportable events with start dates occurring any time after informed consent is obtained until 7 (for non-serious AEs) or 30 days (for SAEs) after the last day of study participation. At each study visit, the investigator will inquire about the occurrence of AE/SAEs since the last visit. Events will be followed for outcome information until resolution or stabilization.

8.3.5 ADVERSE EVENT REPORTING

AEs will be reported to the GBT Medical Affairs Research Program at regular intervals as required by GBT. SAEs will be reported to GBT Pharmacovigilance or Designee and to the IRB within 24 hours after the investigator learns of the event. GBT or Sponsor-Investigator will be responsible for notifying the FDA of any unexpected fatal or life-threatening suspected SAE as soon as possible, but in no case later than 7 calendar days after GBT's initial receipt of the information.

Expected AEs will be recorded in CRFs.

8.3.6 SERIOUS ADVERSE EVENT REPORTING

The study principal investigator will immediately report to GBT Pharmacovigilance or Designee any serious adverse event, whether or not considered study intervention related, including those listed in the protocol or investigator brochure and must include an assessment of whether there is a reasonable possibility that the study intervention caused the event within 24 hours of finding out about the event. Study endpoints that are serious adverse events (e.g., all-cause mortality) must be reported in accordance with the protocol unless there is evidence suggesting a causal relationship between the study intervention and the event (e.g., death from anaphylaxis). In that case, the investigator must immediately report the event to GBT Pharmacovigilance or Designee.

All serious adverse events (SAEs) will be followed until satisfactory resolution or until the PI deems the event to be chronic or the participant is stable. Other supporting documentation of the event may be requested by GBT and should be provided as soon as possible.

GBT Pharmacovigilance or Designee will be responsible for notifying the Food and Drug Administration (FDA) of any unexpected fatal or life-threatening suspected adverse reaction as soon as possible, but in no case later than 7 calendar days after the initial receipt of the information from the study principal investigator. In addition, GBT Pharmacovigilance or Designee must notify FDA and all participating investigators in an Investigational New Drug (IND) safety report of potential serious risks, from clinical trials or any other source, as soon as possible, but in no case later than 15 calendar days after GBT Pharmacovigilance or Designee determines that the information qualifies for reporting.

8.3.7 REPORTING EVENTS TO PARTICIPANTS

Not applicable

8.3.8 EVENTS OF SPECIAL INTEREST

Not applicable

8.3.9 REPORTING OF PREGNANCY

In the event of pregnancy that occurs during study, the pregnancy will be reported to GBT Pharmacovigilance or Designee and the decision for the participant to continue on study or not will depend on the specific situation and will be discussed with GBT Pharmacovigilance or Designee.

8.4 UNANTICIPATED PROBLEMS

8.4.1 DEFINITION OF UNANTICIPATED PROBLEMS (UP)

Since the study intervention is a FDA-approved commercially available medication and CPET is a standardized orderable test, unanticipated problems would not involve risks but rather might be:

- Inability to enroll the expected number of patients, in which case, the possibility of extending the study until 10 patients are enrolled will be discussed with GBT.
- Subject unexpectedly moves away to a location such that travel to the exercise lab is not feasible and can no longer complete the study, in which case, the option of enrolling another subject to maintain the total number of evaluable subjects at 10 will be discussed with the sponsor

8.4.2 UNANTICIPATED PROBLEM REPORTING

The investigator will report unanticipated problems (UPs) to the reviewing Institutional Review Board (IRB) and to the principal investigator (PI). The UP report will include the following information:

- Protocol identifying information: protocol title and number, PI's name, and the IRB project number;
- A detailed description of the event, incident, experience, or outcome;
- An explanation of the basis for determining that the event, incident, experience, or outcome represents an UP;
- A description of any changes to the protocol or other corrective actions that have been taken or are proposed in response to the UP.

To satisfy the requirement for prompt reporting, UPs will be reported using the following timeline:

- UPs that are serious adverse events (SAEs) will be reported to the IRB and to GBT Pharmacovigilance or Designee within 24 hours of the investigator becoming aware of the event.
- Any other UP will be reported to the IRB and to GBT Pharmacovigilance or Designee within 10 days of the investigator becoming aware of the problem.
- All UPs should be reported to appropriate institutional officials (as required by an institution's written reporting procedures), the supporting agency head (or designee), and the Office for Human Research Protections (OHRP) within 10 days of the IRB's receipt of the report of the problem from the investigator.]

8.4.3 REPORTING UNANTICIPATED PROBLEMS TO PARTICIPANTS

Not applicable

9 STATISTICAL CONSIDERATIONS

9.1 STATISTICAL HYPOTHESES

- Primary Efficacy Endpoint(s): Peak VO₂ in the CPET on voxelotor is higher than peak VO₂ in baseline CPET.
- Secondary Efficacy Endpoint(s): Higher peak VO₂ is correlated with improved biochemical markers of sickling and hemolysis.

Paired t-test will be used to evaluate results, as patients are their own controls.

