1 PROTOCOL SUMMARY

1.1 SYNOPSIS

Title:

The Effect of Voxelotor on Exercise Capacity of Youths with Sickle Cell Anemia

Study Description:

This study is a pilot, open-label, single-arm study to evaluate the effect of voxelotor on exercise capacity, as measured by cardiopulmonary exercise testing (CPET) in patients 12 years of age and older with sickle cell anemia (SCA). Voxelotor was recently approved for the treatment of SCA in patients 12 years and older. We hypothesize that exercise capacity will be improved by voxelotor treatment in sickle cell patients whether they are on Hydroxyurea or not. This study will assess exercise capacity by cardiopulmonary exercise testing (CPET) before and after 8 weeks of voxelotor therapy.

Objectives:

Primary Objective: To evaluate the effect of voxelotor on peak oxygen consumption (VO₂) in adolescents with SCA as assessed by change in CPET from baseline.

Secondary Objective: To correlate peak VO₂ with biochemical markers, including hemoglobin, reticulocyte count, bilirubin, lactate dehydrogenase, haptoglobin, % Hgb F expressing cells, P50 oxygen dissociation, point of sickling (POS), and dense cells.

Exploratory Objective: To evaluate the effect of voxelotor on HRQOL as assessed by patient-reported outcome (PGIC) and clinician-reported outcome (CGIC) at end of treatment study visit

Endpoints:

Primary endpoint: Change in Peak VO₂ from baseline

Secondary endpoint: Hemoglobin and biochemical markers of sickling and hemolysis

[figure not shown]
Exploratory endpoint: Clinician and Patient Global Impression of Change assessment (CGIC and PGIC)

Study Population:

1.1.1.1.1 Patients seen in the Pediatric Sickle Cell Program in Northern Virginia (Fairfax, VA) who have a genetically severe forms of sickle cell disease (including Hgb SS, Hgb Sbeta⁰thalassemia, or Hgb SC^{Harlem}) and are age 12 or older.

| | |
|--|--|
| Phase: | This is a single-center, open-label, single-arm longitudinal interventional pilot study. |
| Description of Sites/Facilities Enrolling Participants: | The outpatient sickle cell clinic of Pediatric Specialists of Virginia located in the Schar Cancer Institute on Inova Hospital Campus in Fairfax, VA. This pilot study aims to enroll 10 patients. |
| Description of Study Intervention: | During the open-label treatment period, all participants will receive voxelotor at a fixed dose of 1500mg (administered as three 500mg tablets) orally once daily for 8 weeks |
| Study Duration: | 12 months |

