3 OBJECTIVES AND ENDPOINTS

| OBJECTIVES | ENDPOINTS | JUSTIFICATION FOR ENDPOINTS |
|--|---|--|
| Primary | | |
| Compare peak VO ₂ from sequential CPETs performed on SCA patients before and during voxelotor therapy | Change in Peak VO ₂ from baseline to Week 8 (voxelotor) | The gold standard for exercise capacity is peak VO ₂ . |
| Secondary | | |
| Correlate peak VO ₂ with biochemical markers, including hemoglobin, reticulocyte count, bilirubin, lactate dehydrogenase, haptoglobin, hemoglobin F, % F cells, P50 oxygen dissociation, point of sickling. | Correlation of peak VO ₂ with biochemical markers of sickling and hemolysis | These are established measurements of the biochemical effects of sickling and hemolysis. They will show whether improved exercise capacity is a direct or indirect effect of voxelotor's biochemical activity. |
| Tertiary/Exploratory | | |
| HRQOL assessment | Clinician Global Impression of Change and Patient Global Impression of Change assessments (CGIC and PGIC) | The small number of patients on this pilot study may limit CPET quantitative results from reaching statistical significance. Whether or not peak VO ₂ changes significantly on voxelotor, whether voxelotor has the potential to offer overall clinical improvement and better quality of life can be assessed. |

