9.4.2 ANALYSIS OF THE PRIMARY EFFICACY ENDPOINT(S)

The primary endpoint is peak VO₂, which is a quantitative measurement from the CPET instrument. There will be a single measurement as a baseline and another single measurement after the study drug for each participant. Paired t-test will be used to compare the 2 peak VO₂s.

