9.4.3 ANALYSIS OF THE SECONDARY ENDPOINT(S)

The secondary endpoint is a group of biochemical tests, each with a different scale and different unit of measure. For each biochemical test, there will be a baseline measurement and a measurement after the study drug for each participant. Appropriate statistical comparison will be used for each biochemical measurement.

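### The protocol defines two different secondary endpoints (a correlation with peak VO₂, and the markers themselves), and the paired t-test that 9.1 places under both hypotheses cannot evaluate the correlation

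*Protocol*

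**What the plan says.** The protocol describes the secondary question in six places.

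Four make it an association. The secondary objectives in the synopsis and in Section 3 are to correlate peak VO₂ with a list of markers. The Section 3 endpoint is the correlation of peak VO₂ "with biochemical markers of sickling and hemolysis". The secondary hypothesis in 9.1 is that higher peak VO₂ "is correlated with improved biochemical markers of sickling and hemolysis".

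Two make it the markers alone. The synopsis lists "Secondary endpoint: Hemoglobin and biochemical markers of sickling and hemolysis". Section 9.4.3 says "The secondary endpoint is a group of biochemical tests, each with a different scale and different unit of measure", then "For each biochemical test, there will be a baseline measurement and a measurement after the study drug for each participant", and finally "Appropriate statistical comparison will be used for each biochemical measurement". Peak VO₂ is not mentioned in 9.4.3.

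On method, 9.1 states the primary and secondary hypotheses and then adds one sentence below both: "Paired t-test will be used to evaluate results, as patients are their own controls". Section 9.4.2 gives the same test to the primary endpoint: "Paired t-test will be used to compare the 2 peak" VO₂ values. The sample size is 10 with no power calculation (9.2), and 9.4.1 says results will first be analysed descriptively.

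**The concern.** A correlation between two quantities and a set of before/after marker changes are different endpoints and answer different questions. A reader cannot tell from the protocol which one was pre-specified. An analysis plan can add detail to an endpoint, but it should not have to choose between two.

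The one test named in 9.1 makes this worse. Read where it stands, it covers the secondary hypothesis too, and it does not fit. If hemoglobin and peak VO₂ both rise on average, that does not show that the participants with the larger hemoglobin rise are those with the larger VO₂ rise. Section 3 justifies the markers as showing whether better exercise capacity comes directly or indirectly from the drug's biochemical action. Separate before/after comparisons of each marker say nothing about that link; an association at least addresses it.

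**Working it through.** The protocol gives no alpha, SD or effect size and no figure for this analysis, so there is nothing to reproduce. The check sets the texts side by side and then looks at what each statistic depends on.

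**Step 1. The endpoint in each place**

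| Place | Secondary question | Peak VO₂ involved? |
|---|---|---|
| Synopsis, objective | Correlation | Yes |
| Section 3, objective | Correlation | Yes |
| Section 3, endpoint | Correlation | Yes |
| 9.1, hypothesis | Correlation | Yes |
| Synopsis, endpoint | Markers | No |
| 9.4.3 | Markers, baseline against after drug | No |

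The objective and endpoint disagree within the synopsis itself, and within Section 9 the hypothesis in 9.1 disagrees with the endpoint in 9.4.3.

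**Step 2. What each statistic uses**

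Let x be a participant's change in a marker and y the same participant's change in peak VO₂.

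- Paired t-test on the marker: t = mean(x) / (SD(x)/√n). It uses x only. The test on peak VO₂ uses y only.
- Correlation: r = Σ(x − x̄)(y − ȳ) / √[Σ(x − x̄)² · Σ(y − ȳ)²]. It depends on which x belongs with which y.

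Reassigning the y values among participants leaves both t statistics unchanged but can change r.

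**Step 3. Illustration with invented data, n = 10**

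Hemoglobin changes: 0.2, 0.4, 0.6, 0.8, 0.9, 1.1, 1.2, 1.4, 1.6, 1.8. Mean 1.0, Σ(x − x̄)² = 2.42, SD = √(2.42/9) = 0.519, t = 1.0/(0.519/√10) = 6.10.

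VO₂ changes: −2 to 7 in steps of 1. Mean 2.5, Σ(y − ȳ)² = 82.5, SD = √(82.5/9) = 3.03, t = 2.5/(3.03/√10) = 2.61.

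The denominator of r is √(2.42 × 82.5) = 14.13.

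- Same order: r = 14.1/14.13 = 0.998.
- Reversed: r = −14.1/14.13 = −0.998.
- Order 7, −1, 4, −2, 0, 6, 1, 5, 3, 2: r = 0/14.13 = 0.00.

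The two t values are 6.10 and 2.61 in all three cases.

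**Step 4. The same point by simulation**

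Assumptions: normal changes, n = 10, two-sided 5% tests, 20,000 replicates per case.

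| Mean marker change | True correlation | Paired t-test on marker rejects | Pearson test rejects |
|---|---|---|---|
| 0 | 0 | 4.9% | 5.2% |
| 0 | 0.7 | 5.0% | 68.0% |
| 1 SD | 0 | 80.4% | 4.7% |
| 1 SD | 0.7 | 80.9% | 68.2% |

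The paired test responds to the mean shift and not to the correlation.

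**Step 5. What a correlation could deliver at n = 10**

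Fisher z: the 95% CI is tanh(atanh(r) ± 1.96/√(n − 3)), and 1.96/√7 = 0.741.

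- r = 0.3: −0.41 to 0.78
- r = 0.5: atanh(0.5) = 0.549, limits −0.192 and 1.290, giving −0.19 to 0.86
- r = 0.7: 0.13 to 0.92

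**The case against.** The best defence is that this is loose drafting with little effect. The reason attached to the t-test sentence in 9.1, that patients serve as their own controls, describes a before/after comparison. Section 9.4.2 assigns that test to peak VO₂, and nothing says outright that it will evaluate the correlation. Section 9.4.3 names no test at all. Much of this stands: the sentence may well have been meant for peak VO₂ only. But then it repeats 9.4.2, and its position under both hypotheses still needs limiting. It also leaves the endpoint contradiction untouched.

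A reader might infer more than the documents support:

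- **That the missing correlation coefficient is itself a defect.** The choice of coefficient is commonly left to the analysis plan, which is not at hand.
- **That 9.4.9, which plans no exploratory analyses, rules the correlation out.** The correlation is a secondary objective, so its absence there shows nothing.
- **That the marker values are open to selection because routine labs are drawn at several visits.** The study labs are fixed at Visits 1 and 5 in the Schedule of Activities. Which routine draw to use is ordinary analysis-plan content.
- **That a misleading pair of significant rises is likely.** If the changes are independent, both tests show a significant rise in 38% to 85% of trials when each standardised mean change is 0.8 to 1.2, but in only 0.7%, 1.8% and 8.6% at 0.2, 0.3 and 0.5. The protocol gives no basis for choosing among these, and it nowhere says that two rises would be taken as a correlation.

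**Conclusion.** The point holds as a minor one. The protocol contradicts itself on the secondary endpoint, four places against two, and the test that 9.1 sets under both hypotheses cannot evaluate the correlation. Followed as written, Section 9 would compare each marker before and after and leave the stated secondary hypothesis unanswered.

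This rests on the wording and on the algebra of the two statistics. The invented data and the simulation only illustrate it, and no error rate for this trial is claimed. The consequence is limited: the primary comparison of peak VO₂ is unaffected, the data for a correlation are already collected, and with 10 patients any correlation can be described but not confirmed.

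**What to change.** - **Synopsis, Section 3, 9.1 and 9.4.3:** use one definition of the secondary endpoint.
- **9.1:** confine the paired t-test sentence to the before/after comparison of peak VO₂.
- **9.4.3:** state that the secondary analysis is the correlation, across participants, between change in peak VO₂ and change in each marker, or say explicitly if on-drug levels are meant. Report estimates with 95% confidence intervals, described as descriptive at n = 10. Keep the before/after marker changes as supporting summaries.

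The words *across participants* matter. A repeated-measures (within-participant) correlation with two time points does not centre the changes, so it picks up the mean shifts. In the invented ordering with r = 0.00 it is Σxy/√(Σx²·Σy²) = 25/√(12.42 × 145) = 0.59, which would bring the same confusion back.

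The coefficient and the choice of routine-lab draw can stay with the analysis plan. The cost is wording in four places and a small extra analysis, with no new visits or samples. The drawback is imprecision, as the intervals at n = 10 show.

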9.2 SAMPLE SIZE DETERMINATION

This is a pilot study of 10 patients to define the magnitude of change. Power cannot be calculated at this time.

